A maximum of 36 subjects will be enrolled into the Part 1 safety expansion, and each Part 1 safety expansion cohort will enroll up to 9 evaluable subjects. If < 3 of 9 evaluable subjects have a DLT, then the cohort will be deemed safe. If > 1 safety expansion cohort is deemed safe, then a recommended dose and schedule will be determined in conjunction with the investigators and sponsor based on all available safety, PK, [REDACTED] results. The safety expansion cohorts may be run in parallel to Part 2 and may be limited by the sponsor to subjects with specific tumor types to achieve a balance across cohorts.

Part 2

Part 2 of the study will further evaluate the safety, tolerability, preliminary efficacy, PK, and pharmacologic activity of the recommended dose of INCAGN01949 in subjects with advanced or metastatic adenocarcinoma of the endometrium, ovarian cancer, RCC, melanoma, and NSCLC (squamous and nonsquamous). Each cohort will consist of an individual tumor type. A Simon 2-stage design will be used with a stopping rule to allow for early termination of a particular cohort at the end of Stage 1 if there are insufficient responses observed. During Stage 1, 9 subjects will be enrolled into each cohort; if no responses are observed within a cohort, then the cohort will be discontinued. If at least 1 response is observed, then 8 additional subjects will be enrolled into that cohort (Stage 2), for a maximum of 17 subjects per cohort.

Subjects will continue to receive INCAGN01949 until Protocol-defined withdrawal criteria are met. Continuous evaluation of toxicity events will be performed throughout enrollment in Part 2 of the study. If the cumulative incidence of DLTs occurs in > 33% of subjects after 6 subjects have been observed for at least 28 days, further enrollment may be interrupted until the sponsor has determined the appropriate course of action (eg, the MNTD may be determined). All AEs, regardless of the time of occurrence on study, may be considered in determining of the appropriate dose, schedule, and MNTD.

Toxicity will continue to be monitored throughout the treatment period. If > 33% of subjects (minimum of 6 subjects) experience a Grade ≥ 3 toxicity related to study drug after completing ≥ 4 cycles, then the MNTD will be determined in conjunction with the investigators and sponsor based on all available safety data.

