Estimated Duration of Participation:

Each subject will be expected to participate for up to 14 months.

Estimated Number of Subjects:

Up to approximately 163 subjects may be enrolled in the study.

- Part 1 Dose Escalation – Approximately 18 to 42 evaluable subjects.
- Part 1 Safety Expansion – Approximately 18 to 36 evaluable subjects.
- Part 2 – Up to 85 evaluable subjects (up to 45 in Stage 1 and up to 40 in Stage 2).

Statistical Methods:

This is an open-label, nonrandomized, multicenter, dose-escalation Phase 1/2 study. The primary objective of Part 1 of the study is to determine the MTD and/or PAD of INCAGN01949. The total number of subjects will depend on the number of dose levels tested before the MTD or PAD is established. Dose escalation will follow a 3 + 3 design algorithm.

A Simon 2-stage design will be used in Part 2 with a stopping rule to allow early termination of a particular cohort at the end of Stage 1 if insufficient response is observed (calculated response rate < 5%), while enrolling enough subjects to predict possible target responses ($\geq 25\%$) worthy of cohort expansion and potentially further evaluation in future studies. Part 2 will include 5 cohorts, one for each of the tumor types to be studied (ie, adenocarcinoma of the endometrium, ovarian cancer, RCC, melanoma, and NSCLC). The response rates for each tumor type will be estimated with 95% confidence intervals. Other efficacy variables will be summarized with descriptive statistics.

With a 1-sided Type I error of 0.05 and power of 80%, 9 subjects will initially be enrolled in the first stage. If no responses are observed within a cohort (consistent with a calculated response rate < 5%), the cohort will be discontinued. If at least 1 response is observed within a cohort, then 8 additional subjects will be enrolled in the appropriate cohort to a maximum of 17 subjects per cohort. Investigation of the study drug will be considered interesting (predictive of a 25% response rate) if ≥ 3 responses are observed in the first 17 subjects.

TABLE OF CONTENTS

SYNOPSIS	3
LIST OF ABBREVIATIONS.....	19
1. INTRODUCTION	22
1.1. Background.....	22
1.1.1. The Role of the Immune System in Cancer.....	22
1.1.2. Immune Modulators.....	23
1.1.3. OX40 and the Tumor Necrosis Factor Super Family	23
1.1.4. In Vitro and In Vivo Evaluation of OX40.....	24
1.1.5. Clinical Experience With OX40 Agonists.....	25
1.2. Overview of INCAGN01949.....	26

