4.1.1.1. Dose Escalation

In the dose-escalation part of the study, a 3 + 3 design will be utilized to determine the MTD or PAD of INCAGN01949. A minimum of 3 evaluable subjects will be enrolled in each cohort beginning with Cohort 1 (7 mg; starting dose). There will be a waiting period of 48 hours between dose administration to the first subject and second subject of each dose cohort. The first 3 subjects enrolled within a cohort will be observed for a DLT observation period of 28 days before the next cohort begins enrollment. The dose will be escalated if 0 of the first 3 evaluable subjects enrolled has a DLT. If 1 of the first 3 evaluable subjects enrolled has a DLT, then the cohort will be expanded to include 3 additional evaluable subjects, and if no DLT occurs in the additional 3 subjects, then the dose will be escalated. If a DLT occurs in one-third or more of the expanded cohort, then the MTD will be deemed to be exceeded, and the previous dose level will be considered the MTD. If only 3 subjects were treated at the MTD or PAD, then a minimum of 3 additional subjects will be enrolled before this dose is administered in Part 2 of the study.

If Cohort 1 (7 mg; starting dose) exceeds the MTD, then the sponsor and investigators will consider administering INCAGN01949 at 2 mg (Cohort -1) and/or investigate 7 mg at alternate dose schedules (eg, every 3 week administration), based on available safety, PK, [REDACTED] data. If an alternate schedule is tested and determined to be safe, then re-escalation of INCAGN01949 will proceed according to [Table 2](#).

Throughout the treatment period, if > 33% of subjects (a minimum of 6 subjects) experience a Grade \geq 3 toxicity related to study drug after completing \geq 4 cycles, then dose administration will be stopped, and the MNTD will be determined in conjunction with the investigators and sponsor based on all available safety data.

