4.1.1.2. Safety Expansion

In order to evaluate additional [REDACTED] activity of INCAGN01949 and confirm the preliminary safety of the dose-escalation cohorts, Part 1 of the study may include safety expansion cohorts evaluating doses and schedules equivalent to or lower than the highest dose levels determined to be safe and/or doses determined to be pharmacologically active. The alternative dose administration schedules and fixed doses (equivalent to or less than the MTD determined during dose escalation) that may be explored during the safety expansion would depend on PK, [REDACTED] and safety results.

A maximum of 36 subjects will be enrolled into the Part 1 safety expansion, and each Part 1 safety expansion cohort will enroll up to 9 evaluable subjects. If < 3 of 9 evaluable subjects have a DLT, then the cohort will be deemed safe. If > 1 safety expansion cohort is deemed safe, then a recommended dose and schedule will be determined in conjunction with the investigators and sponsor based on all available safety, PK, [REDACTED] results. The safety expansion cohorts may be run in parallel to Part 2 and may be limited by the sponsor to subjects with specific tumor types to achieve a balance across cohorts.

4.1.2. Part 2

[figure not shown]
Part 2 of the study will further evaluate the safety, tolerability, preliminary efficacy, PK, and pharmacologic activity of the recommended dose of INCAGN01949 in subjects with advanced or metastatic adenocarcinoma of the endometrium, ovarian cancer, RCC, melanoma, and NSCLC (squamous and nonsquamous). Each cohort will consist of an individual tumor type. A Simon 2-stage design will be used with a stopping rule to allow for early termination of a particular cohort at the end of Stage 1 if there are insufficient responses observed. During Stage 1, 9 subjects will be enrolled into each cohort; if no responses are observed within a cohort, then the cohort will be discontinued. If at least 1 response is observed, then 8 additional subjects will be enrolled into that cohort (Stage 2), for a maximum of 17 subjects per cohort.

Subjects will continue to receive INCAGN01949 until Protocol-defined withdrawal criteria are met. Continuous evaluation of toxicity events will be performed throughout enrollment in Part 2

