
 • \geq Grade 2 ocular irAEs will be considered a DLT. • Grade 3 irAEs that do not improve to baseline or at least Grade 1 in < 5 days with appropriate care or with corticosteroid therapy will be considered a DLT. • Grade 4 irAEs will be considered a DLT regardless of duration.
General

 • Inability to receive the planned number of doses within the 28-day DLT period due to toxicity, regardless of grade, will be considered a DLT.
MTD

 • In Part 1 of the study, the MTD will be defined as 1 dose level below that at which \geq one-third of subjects in a particular cohort have DLTs. • In Part 2 of the study, toxicities will continue to be monitored. If the cumulative incidence of DLTs occurs in $\geq 33\%$ of subjects after 6 subjects have been observed for at least 28 days, further enrollment may be interrupted, and the investigators and sponsor will meet and reassess the MTD. All AEs, regardless of the time of occurrence on study, may be considered in DLT determination purposes.
MNTD

 • For each dose and schedule explored, if $> 33\%$ of subjects (minimum of 6 subjects) experience a \geq Grade 3 toxicity related to study drug after completing ≥ 4 cycles, then treatment will be stopped, and the MNTDs will be determined in conjunction with the investigators and sponsor based on all available safety data. All AEs, regardless of the time of occurrence on study, may be considered in DLT determination decisions.

Note: Transient (≤ 72 hours) abnormal laboratory values without associated clinically significant signs or symptoms based on investigator determination will not be considered DLTs.

^a Immune-related AEs are a diagnosis of exclusion, after alternative etiologies have been ruled out.

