9.2. Selection of Sample Size

9.2.1. Sample Size in Part 1

The primary objective of Part 1 of the study is to determine the PAD or the MTD of INCAGN01949. The total number of subjects will depend on the number of dose levels tested before the PAD or MTD is established. Approximately 18 to 42 subjects (6 subjects per dose level for 7 dose levels) will be included based on the dose escalation. Dose escalation will follow the 3 + 3 design algorithm. Based on this algorithm, a minimum of 3 evaluable subjects will be enrolled in each cohort beginning with Cohort 1 (7 mg; starting dose) and a maximum of 6 subjects for each cohort.

Part 1 of the study may also include safety expansion cohorts evaluating dose(s) and schedule(s) equivalent to or lower than the highest dose levels determined to be safe and/or doses determined to be pharmacologically active. Each safety expansion cohort will enroll 9 evaluable subjects. Up to 36 subjects will be enrolled in Part 1 safety expansion. If < 3 of 9 evaluable subjects experience a DLT, then the cohort will be deemed safe. If more than 1 safety expansion cohort is deemed safe, then a recommended dose and schedule will be determined in conjunction with the investigators and sponsor based on all available safety, PK, [REDACTED] results.

9.2.2. Sample Size in Part 2

Part 2 of the study will further evaluate the safety, tolerability, preliminary efficacy, PK, and pharmacologic activity of the recommended dose of INCAGN01949. The sample size for each tumor type will be guided by the Simon 2-stage design (Simon 1989). Let 5% be a clinically insignificant response rate for all tumor types. During Stage 1, 9 subjects will be enrolled; if no responses are observed, then the cohort will be discontinued. If at least 1 response is observed, then 8 additional subjects will be enrolled (Stage 2), for a maximum of 17 subjects per tumor type in Part 2. The detailed calculation is based on a 1-sided Type I error of 0.05 and power of 80% to detect a 25% response rate for each of the tumor types.

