9.6. Interim Analysis

Part 1 of the study will use a standard 3 + 3 dose-escalation design. Each Part 1 safety expansion cohort will enroll up to 9 additional evaluable subjects. If < 3 of 9 additional evaluable subjects has a DLT, then the cohort will be deemed safe. If more than 1 safety expansion cohort is deemed safe, then a recommended dose and schedule will be determined in conjunction with the investigators and sponsor based on all available safety, PK, [REDACTED] results. The probability of declaring a dose cohort as safe for various DLT rates in the 3 + 3 and the safety expansion is summarized in [Table 17](#).

Table 17: Probability of Dose Escalation by DLT Rate for 3 + 3 Design and Safety Expansion

True DLT Rate	Probability of Declaring Dose Cohort as Safe	
	3 + 3 Design	In BOTH 3 + 3 Design and Safety Expansion
10%	90.6%	85.8%
20%	70.9%	52.3%
30%	49.4%	22.9%
40%	30.9%	7.2%
50%	17.2%	1.5%
60%	8.2%	0.2%

In Part 2, the Simon 2-stage design will be applied. During Stage 1, 9 subjects will be enrolled, and if no responses are observed, then the cohort will be discontinued. The probability of early termination for Stage 1 is summarized in [Table 18](#). If at least 1 response is observed, then 8 additional subjects will be enrolled (Stage 2).

Table 18: Probability of Early Termination at Stage 1 for Simon 2-Stage Design

True Response Rate	Probability of Early Termination at Stage 1
15%	23.2%
20%	13.4%
25%	7.5%
30%	4.0%
35%	2.1%

Subjects will continue to receive INCAGN01949 until Protocol-defined withdrawal criteria are met. Continuous evaluation of toxicity events will be performed throughout enrollment in Part 2 of the study. If the cumulative incidence of DLTs occurs in $\geq 33\%$ of subjects after 6 subjects have been observed for at least 28 days, further enrollment may be interrupted until the sponsor has determined the appropriate course of action. All AEs, regardless of the time of occurrence on study may be considered in determination of the appropriate dose, schedule, and MNTD.

Toxicity will continue to be monitored throughout the treatment period. If $> 33\%$ of subjects (minimum of 6 subjects) experience a Grade ≥ 3 toxicity related to study drug after completing ≥ 4 cycles, then dose administration will be stopped, and the MNTD will be determined in conjunction with the investigators and sponsor based on all available safety data.

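### No rule closes a Part 1 safety expansion cohort at its third DLT, although the cohort can then no longer be deemed safe

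*Protocol*

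**What the plan says.** The decision rule appears in the protocol synopsis, 4.1.1.2, 9.2.1 and 9.6, and in SAP 3.1.2 and 3.4.1, always with a denominator of 9: "If < 3 of 9 evaluable subjects have a DLT, then the cohort will be deemed safe".

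The cohort size varies. The synopsis and 4.1.1.2 say that "each Part 1 safety expansion cohort will enroll up to 9 evaluable subjects", and SAP 3.1.2 agrees. Section 9.6 has "Each Part 1 safety expansion cohort will enroll up to 9 additional evaluable subjects". Section 9.2.1 says "Each safety expansion cohort will enroll 9 evaluable subjects", and SAP 3.4.1 follows it.

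The overall limit also varies. Section 4.1.1.2 states "A maximum of 36 subjects will be enrolled into the Part 1 safety expansion", and 9.2.1 likewise counts subjects enrolled. The synopsis list of subject numbers and 4.3.1 give "Part 1 Safety Expansion – Approximately 18 to 36 evaluable subjects".

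Table 3 in 5.4.2 carries a general criterion, which begins "In Part 1 of the study, the MTD will be defined as 1 dose level below that at which" and goes on to a DLT proportion of one-third or more in a particular cohort.

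Section 8.7 provides sponsor-investigator calls in Part 1 about once a week, with no numeric trigger. In Part 2, 4.1.2 allows enrollment to be interrupted on the cumulative DLT rate once 6 subjects have been observed for 28 days.

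**The concern.** After a third DLT the remaining places in a cohort cannot change its result. Subjects entered from then on are exposed to a dose and schedule that has already failed its safety criterion.

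The stages on either side have a written checkpoint. The 3+3 observes its first 3 subjects for 28 days before the next cohort opens and decides at 3 and at 6. Part 2 has its cumulative trigger. The safety expansion has neither, although 4.1.1.2 lets it explore alternative schedules, which need not have passed through the 3+3. The MNTD rule does not fill the gap, because it concerns related Grade 3 or higher toxicity after at least 4 cycles.

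A second, smaller matter is the cohort that ends below 9. The text allows it, but neither the decision rule nor Table 17 covers it.

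**Working it through.** **Inputs.** The safety expansion rule is at most 2 DLTs in 9 (4.1.1.2). The 3+3 passes a dose on 0 of 3, or on 1 of 3 followed by 0 of 3 (4.1.1.1). The stated operating characteristics are in Table 17 (9.6; SAP Table 2). Write p for the true DLT rate and q = 1 − p.

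**Step 1: reproduce Table 17.** The probability of passing the 3+3 is q³ + 3pq²·q³. The probability of passing the expansion is P(X ≤ 2) for X binomial(9, p). The probability of passing both is the product. At p = 0.30:

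- 3+3: 0.343 + 0.441 × 0.343 = 0.494
- expansion: 0.0404 + 0.1557 + 0.2668 = 0.463
- both: 0.494 × 0.463 = 0.229, which is the printed 22.9%

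All 12 entries agree to the printed decimal with n fixed at 9.

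**Step 2: when the third DLT arrives.** P(third DLT at subject k) = C(k−1, 2)·p³·q^(k−3) for k = 3 to 9. At p = 0.30 these are 0.0270, 0.0567, 0.0794, 0.0926, 0.0972, 0.0953 and 0.0889. They sum to 0.537 = 1 − 0.463, so a cohort that reaches a third DLT is exactly a cohort that fails. Closing it then cannot alter any probability of being deemed safe.

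**Step 3: subjects spared per cohort.** With each outcome known before the next entry, the mean is the sum of (9 − k) × P(third DLT at k). At p = 0.30 that is 0.162 + 0.284 + 0.318 + 0.278 + 0.194 + 0.095 = 1.33.

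With entry in blocks of 3 and outcomes awaited between blocks, the mean is 3 × P(third DLT by subject 3) + 3 × P(third DLT by subject 6). At p = 0.30 that is 3 × (0.027 + 0.256) = 0.85.

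| True DLT rate | Passes 3+3 | < 3 of 9 | Both (matches Table 17) | Third DLT before 9th subject | Mean spared, one at a time | Mean spared, blocks of 3 |
|---|---|---|---|---|---|---|
| 10% | 90.6% | 94.7% | 85.8% | 3.8% | 0.09 | 0.05 |
| 20% | 70.9% | 73.8% | 52.3% | 20.3% | 0.54 | 0.32 |
| 30% | 49.4% | 46.3% | 22.9% | 44.8% | 1.33 | 0.85 |
| 40% | 30.9% | 23.2% | 7.2% | 68.5% | 2.28 | 1.56 |
| 50% | 17.2% | 9.0% | 1.5% | 85.6% | 3.22 | 2.34 |
| 60% | 8.2% | 2.5% | 0.2% | 95.0% | 4.05 | 3.11 |

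These means are over all cohorts, including those that pass.

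**Step 4: cohorts that end short.** Two DLTs are 2/6 = 33% at n = 6, but 29%, 25% and 22% at n = 7, 8 and 9. A count of 2 therefore meets the Table 3 criterion only at n = 6 or fewer. Three DLTs meet it at every n up to 9, since 3/9 is exactly one-third.

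For a cohort that ends at 6, the one-third criterion passes at most 1 DLT. At p = 0.40 that gives 0.6⁶ + 6 × 0.4 × 0.6⁵ = 23.3%, against 23.2% at n = 9. At p = 0.30 it gives 42.0% against 46.3%.

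**Step 5: the cap.** Four cohorts of 9 use all 36 places. If the cap counts subjects enrolled, no replacement under 4.3.2 is possible. The documents give no replacement rate. At an assumed 5% or 10%, the probability that none of 36 needs replacing is 0.95³⁶ = 16% or 0.90³⁶ = 2%. With three cohorts there are 36 − 27 = 9 spare places.

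**The case against.** The sponsor can already stop a failing cohort. The calls in 8.7 cover de-escalation and cohort expansion decisions, 5.4.5 adds adjudication of high-grade events as potentially dose-limiting, and up to 9 is a ceiling rather than a target. The Part 2 trigger is itself permissive in the protocol. This stands as far as it goes: what is missing is a written trigger, not the ability to stop.

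The savings are also modest where the drug is tolerable (0.1 and 0.5 subjects at 10% and 20%). A dose with a true rate of 40%, 50% or 60% passes the 3+3 only 30.9%, 17.2% or 8.2% of the time. With concurrent entry, subjects may be dosed before an earlier DLT is known. All of this limits the size of the gain without removing it, and the 3+3 filter does not protect a schedule that skipped the 3+3.

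A reader might also infer that a cohort closed at 2 DLTs in 6 would be deemed safe, with a probability of 54.4% at a true rate of 40% instead of 23.2%. The documents do not support that. The rule is never written as fewer than 3 DLTs without the 9. Table 3 is worded for Part 1, which the synopsis and 4.1 define to include the safety expansion; on that reading 2 of 6 reaches the one-third limit and fails. The 54.4% applies only if a bare count were used. What remains is that neither document says which text governs a short cohort.

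**Conclusion.** The gap is real. A third DLT settles a safety expansion cohort, no written rule then closes enrollment, and 9.2.1 read literally fills the cohort to 9. Table 17 is correct, and this is not an error in the decision rule.

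The gain from closing is at most 0.1 to 4.0 subjects per cohort over true DLT rates of 10% to 60%. That upper bound rests on independent subjects with a common DLT rate and on each DLT being known before the next entry. Entry in blocks of 3 with outcomes awaited gives about 0.05 to 3.1. The protocol prescribes neither pattern for the expansion, so the realised saving may be smaller.

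The short cohort is an unreconciled case, not a permission to declare a dose safe. The difference between enrolled and evaluable subjects in the cap is a genuine mismatch that matters mainly if all four cohorts open.

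**What to change.** In protocol 4.1.1.2 (and the matching synopsis text), 9.2.1 and 9.6, and in SAP 3.1.2 and 3.4.1, state that enrollment to a safety expansion cohort closes at its third DLT. This costs one sentence, adds no subjects and leaves Table 17 as printed.

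In the same edit:

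- Settle the cohort size. Either require 9 DLT-evaluable subjects for a declaration of safe, except where fewer than 3 DLTs in 9 is already certain (0 in 7, or at most 1 in 8), or state that the one-third criterion in Table 3 governs a cohort that ends short. The first keeps the decision probabilities in Table 17; the second needs operating characteristics for n below 9.
- State whether the cap of 36 counts enrolled or DLT-evaluable subjects, and use the same term in the synopsis, 4.1.1.2, 4.3.1, 9.2.1 and SAP 3.1.2 and 3.4.1. Counting evaluable subjects costs at most the replacements that 4.3.2 already allows.

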NSAID	nonsteroidal anti-inflammatory drug
NSCLC	non-small cell lung cancer
PAD	pharmacologically active dose
PCP	pneumocystis pneumonia
█	██████████
PD-1	programmed cell death protein
PFS	progression-free survival
PK	pharmacokinetic
PR	partial response
PT	prothrombin time
RCC	renal cell carcinoma

Abbreviation	Definition
RECIST	Response Evaluation Criteria in Solid Tumors
RNA	ribonucleic acid
SAE	serious adverse event
SD	stable disease
SSD	safe starting dose
SUSAR	suspected unexpected serious adverse reaction
TCR	T-cell receptor
TEAE	treatment-emergent adverse event
TNF	tumor necrosis factor
TNFR	tumor necrosis factor receptor
Treg	regulatory T cell
ULN	upper limit of normal

